
[figure not shown]
Specific Aims

- Aim 1: To investigate the efficacy of active FES vs. passive FES, as measured by changes in behavioral measures. Hypothesis: We hypothesize that improvements in motor function will be significantly greater using the active FES therapy than the passive FES therapy.
- Aim 2: To investigate the relationship between brain functional activation patterns and behavior changes induced by active vs. passive FES intervention. Hypothesis: We hypothesize that changes induced by active FES (as measured by brain fMRI and EEG measures) will show greater adaptive brain reorganization changes (i.e. brain changes that correlate with improved outcomes) than that induced by the passive FES.
- Aim 3: To investigate the relationship between brain white matter integrity and behavior changes induced by active vs. passive FES intervention. Hypothesis: We hypothesize that changes induced by active FES (as measured by brain DTI measures) will show greater adaptive brain reorganization changes (i.e. brain changes that correlate with improved outcomes) than that induced by the passive FES.

Research Design and Methods

This is a prospective, longitudinal study in which stroke patients with upper-limb hemiparesis will be adaptively randomized to two groups: **Active FES (aka the experimental group)**, and **Passive FES aka (the control group)**. Adaptive randomization in our study will be done based on age and severity of UE impairment (see Figure 1).

Participants: 144 patients will be enrolled in the study following inclusion/exclusion criteria below:

Inclusion criteria: ages 50-85 years; new-onset ischemic stroke 12 months prior – chronic time frame; right hand dominant – affected arm; mild to moderate unilateral upper extremity(UE) impairment (Action Research Arm Test; ARAT score > 35) or severe unilateral upper extremity(UE) impairment (ARAT score <= 35); no upper extremity injury or conditions that limited use prior to the stroke; pre-stroke independence with a Modified Rankin Score of 0 or 1, and the ability to provide informed consent on their own behalf.

Exclusion criteria: Inability to competently participate in study procedures, Concurrent upper extremity therapy, other neurological (e.g., AD) or psychiatric disorders.

Note, participants with contraindications to MRI will continue to be eligible for this research and will be asked to participate in both the computer training and the behavioral assessments.

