During the COVID-19 pandemic, preliminary visits will be stopped and consent procedures will be conducted by phone, when possible, to minimize face-to-face contact subjects have with the research team. A copy of the consent form will be mailed or emailed to subjects prior to the scheduled consent phone call. If emailed, the consent form will be encrypted, if mailed, two copies will be provided. A study team member will call potential subjects at the scheduled time to review the information in the consent form including study procedures, risks associated with participation, alternatives to participation and whom to contact for additional information. Any questions will be addressed during the course of the phone call and

subjects will be encouraged to contact the study team with any questions or concerns they might have at any time. Upon completion of the consent process, a copy of the signed consent form will be provided in one of the following ways depending on each subject preferences and capabilities:

- Electronic signature will be provided using DocuSign
- Subject will be asked to scan a copy of the entire consent document and email it back to the study team.
- Subject will be asked to take a photo of the signature page and email a copy to the study team.
- If subjects are unable to provide an electronic copy of the signed consent form, they will be asked to bring a copy of the form to the research visit.

Prior to the start of any study procedures, all subjects will be reminded that participation is optional and they can change their mind at any time.

All patients that agree to participate will be asked to complete behavioral assessments and optional MRI scans at 5 time points. They will also be required to participate in 15 intervention sessions.

Patients with contraindications to MR will still have the option of being included in this research. They will be asked to complete all but the MR imaging.

Study Procedures

A) Behavioral Assessment:

The following commonly used measures of upper extremity motor assessment, standard stroke scales, and measure of activities of daily living will be administered at five timepoints to all patients over the length of the study.

1. The Fugl-Meyer (FM) motor assessment is used to measure voluntary limb movement. It includes the upper extremity (UW0 subscale (33 items; score range 0 – 66) and the lower extremity (LE) subscale (17 items; score range, 0-34) for a total motor FM score of 100.

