Active FES (the experimental group): Training will involve trials of actual or attempted hand movement alternating with periods of rest. Patients will be trained to control a cursor on a computer screen using motor-related cortical activity. EEG electrodes will be attached to the patient’s scalp using a standard, commercially available electrode cap. We will use the general purpose, freely available BCI computer program “BCI2000” to control signal acquisition, signal processing, and feedback to the participant. The EEG-BCI system will be connected to a FES device and the FES electrodes will be placed on the stroke-affected arm. Electrode placement is similar to that described above for the patients in the passive FES group. The electrodes will be connected to commercially available stimulus isolator units, which ensure clean, opto-electrical isolation. The aim is to elicit motor response in the affected hand in all of the

fingers as evenly as possible. The appropriate level of stimulation that is both comfortable for the participant and sufficiently produces visible movement in the affected hand is estimated and recorded for use in the current and future sessions. All patients will complete 2-3 study visits per week (up to a maximum of 15 sessions) with each session or study visit lasting for about 2 hours.

Study procedures [behavioral visits and intervention] will be photographed and visibly and audibly recorded. Permission will be obtained from the participant before photographs/recording are commenced. The pictures/recording may be used in the following ways:

- in lab meetings to discuss the participant's progress and possible ways to improve testing
- to assess inter-tester reliability and for training new personnel before they administer the behavioral tests
- in research group presentations with collaborators or at conferences to show examples of participants performing the tasks in this research study

Compensation for study participation

All patients will be compensated up to \$500 for completing the entire study. Payment of up to \$100 (\$60 for completing the MRI scan and \$40 for completing the behavioral testing) will be provided at the end of each of the five study assessment time-points.

Note since MR scanning is optional, we will offer \$60 for each MR scan and \$40 for each behavioral assessment/testing session at each visit (\$60 for MR scan + \$40 for assessment/testing = \$100 per visit X 5 = \$500).

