For Specific Aim 2: To track fMRI and EEG-BCI based brain reorganization changes and behavioral changes induced by active vs. passive FES. Changes in fMRI and EEG derived LI values over time will be compared in the 2 groups. Group differences in LI at each time-point will be evaluated using Mann-Whitney U test. To determine if there are significant main effects for groups and time, and significant interaction of Group X Time, we will perform Linear Mixed Model analyses. To test if change in fMRI and EEG derived LI, across multiple time-points correlate with change in behavioral measures: The difference in each measure, example from time-point 1(T1) to T2 (i.e. change score, Δ LI) will be calculated and separate correlation (Pearson or Spearman rho) analyses will be performed to see if change in fMRI and EEG significantly correlate with change in behavioral scores (Δ ARAT or Δ SIS-hand function etc).

EEG Data Statistical Analysis: The independent variables are the signed r-squared values and the coherence estimates. At individual participant level the data consists of average estimates per session for condition/movement/screening phase combination sets, and at group level the estimates consist of grand averages over sessions of each individual participant data in the group. Nonparametric statistical tests will be run by calculating Monte-Carlo estimates of the significance probabilities and critical values from the permutation distribution (Oostenveld et al., 2007), followed by correction for multiple comparison using false discovery rate (FDR). Our priori hypotheses regarding expected changes in the r-squared values and coherence as a result of intervention at C3 and C4 sites will be tested using paired t-tests in MATLAB.

For Specific Aim 3: To track DTI based brain reorganization changes and behavioral changes induced by active vs. passive FES. The Pearson r or non-parametric Spearman rank correlation test, as appropriate, will

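### For signed r-squared and coherence, the planned session averages dilute change across training, and no stated analysis compares that change between active and passive FES

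*Combined protocol and SAP*

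**What the plan says.** Specific Aims, Aim 2, poses a between-arm question about change: "We hypothesize that changes induced by active FES (as measured by brain fMRI and EEG measures) will show greater adaptive brain reorganization changes" than passive FES. Aim 2 counts a change as adaptive when it correlates with improved outcome. This point concerns the first step, comparing the change itself between arms.

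Under Data Processing/Data Analysis, the EEG Data Statistical Analysis paragraph of Specific Aim 2 names the variables: "The independent variables are the signed r-squared values and the coherence estimates". It describes two levels of data. First, "At individual participant level the data consists of average estimates per session for condition/movement/screening phase combination sets". Second, "at group level the estimates consist of grand averages over sessions of each individual participant data in the group". I read the second as one averaged value per patient for each combination. Permutation tests with FDR correction follow, but the paragraph does not say what they contrast. It then adds paired t-tests for expected changes in both variables at C3 and C4, without naming the time points that are paired.

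On the number of sessions, the Active FES part of the Intervention section says "All patients will complete 2-3 study visits per week (up to a maximum of 15 sessions"), while the end of Subject Recruitment says "They will also be required to participate in 15 intervention sessions". The analysis section has no rule for a patient whose session series is incomplete.

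**The concern.** A value averaged over the whole course of training is not a measure of change. It combines where the patient started with part of what happened afterwards. If such averages are the only group-level data for r-squared and coherence, an arm difference cannot be read as a difference in reorganisation, and a real difference in change is harder to see.

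The starting level matters here because the training tasks differ. Active FES patients learn to control a cursor with motor-related cortical activity. Passive FES patients have EEG recorded during movement trials, with no cursor control described. A constant effect of the task on the recording would enter a session average in full but would cancel in a change measure.

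At stake is part of Aim 2: whether these two variables can support its EEG hypothesis. The primary outcome, ARAT, is not affected.

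**Working it through.** The plan states no figure for this analysis, so there is none to reproduce. The check has four steps.

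**1. Which planned analysis covers which variable (Specific Aim 2)**

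| Analysis | Variable | Change over time? | Active vs passive? |
|---|---|---|---|
| Mann-Whitney at each time point | fMRI and EEG LI | No, one time point at a time | Yes |
| Linear mixed model, Group x Time | fMRI and EEG LI | Yes | Yes |
| Correlation of change with behaviour | fMRI and EEG LI | Yes | Not stated |
| Permutation tests with FDR | r-squared, coherence | Grand average over sessions | Not stated |
| Paired t-tests at C3 and C4 | r-squared, coherence | Yes, time points not named | No, within patient |

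Neither row for r-squared and coherence compares change between arms.

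**2. What the average keeps**

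Assume a patient starts at level B and gains D by session 15. The size of D and the shape of the course are assumptions; the documents give neither. For a linear course, session s has value B + D(s-1)/14. The mean over the first k sessions is then B + D(k-1)/28:

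- k = 15: 14/28 = 0.50 D
- k = 10: 9/28 = 0.32 D
- k = 5: 4/28 = 0.143 D

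The arm difference in 15-session averages is therefore (difference in B) + 0.50 x (difference in D). With t = s-1, three other shapes were tried: an early plateau, (1-exp(-t/3))/(1-exp(-14/3)); a step at session 8; and a late rise, (t/14)^3. They keep 0.77, 0.53 and 0.27 D.

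**3. Incomplete series, if included**

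Assume the same true course in both arms, with a share p of one arm only stopping after session 5. The spurious arm difference is p x (15-session mean minus 5-session mean). For the linear course this is 0.10 x (0.500-0.143) = 0.036 D and 0.20 x 0.357 = 0.071 D.

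| Course | Mean of 15 | Mean of first 5 | Gap | p = 10% | p = 20% |
|---|---|---|---|---|---|
| Linear | 0.500 | 0.143 | 0.357 | 0.036 | 0.071 |
| Early plateau | 0.774 | 0.432 | 0.342 | 0.034 | 0.068 |
| Step at session 8 | 0.533 | 0.000 | 0.533 | 0.053 | 0.107 |
| Late rise | 0.268 | 0.007 | 0.261 | 0.026 | 0.052 |

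All entries are in units of D. If both arms stop alike, the difference is zero.

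**4. Noise of a change measure**

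Let b be the between-patient SD of the level and w the session-to-session SD, with no variation in slope between patients (an assumption). The 15-session average has variance b² + w²/15. The mean of the last three sessions minus the mean of the first three has variance 2w²/3, and under the linear course it carries 13/14 - 1/14 = 0.857 D instead of 0.50 D. The change measure thus takes on ten times the session noise variance (2/3 against 1/15) but sheds b². The two have equal signal-to-noise when 0.25/(b² + w²/15) = 0.735/(0.667w²). This gives b² = 0.160w², or b = 0.40w. Below that ratio the average is the more powerful; above it, the change measure is.

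**The case against.** The strongest reply is that Aim 2's EEG question is answered elsewhere in the same section. EEG-derived LI is compared between groups over time with a Group x Time model, and change in r-squared and coherence has its own tests at C3 and C4. This stands in part. A reader might infer that Aim 2 has no between-arm EEG analysis of change at all, and the LI model shows that this is wrong. It does not help r-squared and coherence, whose only change test has no group term. Significance in one arm and not in the other would not show that active FES changes more.

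A reader might also infer that averaging removes the training effect, so that these tests could never detect it. The documents do not support that. With starting levels equal on average after randomisation, a true arm difference in D would still appear, diluted. When patients differ little in level, the average may even be the more sensitive summary.

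Third, the paragraph does not say that the permutation tests compare active with passive. They may contrast conditions, movements or phases within a group. The screening-phase label is undefined and might keep some time structure. This is fair, but it leaves the gap open: if the contrast is between arms, it compares diluted levels; if it is not, these variables have no stated arm comparison.

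Finally, early stopping. A reader might infer that patients who stop early bias the arm comparison. Nothing says that they enter the average, one section requires all 15 sessions, and the only loss figure (10%, in Sample size considerations) combines drop-out with poor-quality data and is not split by arm. What stands is only that the rule is missing.

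**Conclusion.** The point holds for signed r-squared and coherence only. Their group-level summary dilutes change and mixes it with the starting level, and no stated analysis compares their change between active and passive FES. That conclusion follows from the text and needs no assumption about the data. How much of the change survives does rest on assumption: 0.50 D for a linear course and 0.27 to 0.77 D across the shapes tried.

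Bias from incomplete series is secondary and modest. It requires that such patients are included and that stopping differs by arm. At 10-20% of one arm stopping at session 5, it is about 0.04-0.07 D for a linear course and 0.03-0.11 D across the shapes tried.

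The change is worth making because it is cheap and lets these variables address Aim 2. It does not bear on the efficacy conclusion from ARAT.

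**What to change.** Fit the per-session r-squared and coherence estimates in a linear mixed model with Group, session number and Group x session, using every session a patient completed. The Group x session term is the between-arm test of change. Alternatively, compute each patient's late-minus-early change over a session window common to both arms, and compare arms by permutation with the planned FDR correction.

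In the same paragraph:

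- keep the grand average over sessions as a descriptive summary only;
- name the contrast of the permutation tests and the time points paired in the C3 and C4 t-tests;
- define the screening-phase label;
- state how incomplete session series are handled, and report the number of sessions contributed by arm.

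The statements on the number of sessions in Subject Recruitment and in the Intervention section must be reconciled.

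The cost is analysis wording and modest programming. The plan already forms per-session estimates and records EEG in both arms, so no new data are needed. The downside is that a change measure carries more session-to-session noise than an average over all sessions. The mixed model limits this by using every session rather than a few at each end.

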Passive FES (the control group): Functional Electrical Stimulation (FES) of the upper extremity is delivered through a pair of 2” x 2” square electrodes, commercially available stimulus isolator units, which ensure clean, opto-electrical isolation, placed securely on the affected forearm using highly conductive Electrolyte Spray and produced by the LG-7500 Digital Muscle Stimulator (LGMedSupply, Cherry Hill, NJ, USA). The electrodes are placed in half the sessions, superficial to flexor digitorum superficialis to facilitate hand and finger flexion, and in the other half of the sessions superficial to extensor digitorum communis to facilitate hand and finger extension.

Stimulation is controlled through the PC using an Arduino Uno R3 (Adafruit Industries, New York, NY, USA) and a simple reed relay circuit, with the amplitude set to elicit observable muscle activation (e.g. finger grasping) without pain. The pulse rate of the stimulation is set to 60Hz in order to produce tetanic contraction of the muscle and the pulse width is set to 150 μ s. The input signal will initially be set to zero and adjusted in steps of 5 mA, with allowable stimulation up to 50 mA. All parameters will be adjusted to the patients’ comfort level, and testing will be interrupted immediately should a patient report any discomfort.

Training will involve trials of actual or attempted hand movement alternating with periods of rest. Brain activity will be simultaneously recorded using EEG (electroencephalography) technique. EEG electrodes will be attached to the patient’s scalp using a standard, commercially available electrode cap.

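### For signed r-squared and coherence at C3 and C4, the only test assigned to the a priori EEG hypotheses is a within-patient paired t-test, which cannot address Aim 2's comparison of active with passive FES

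*Combined protocol and SAP*

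**What the plan says.** All references are to the combined protocol and SAP.

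- **Specific Aims, Aim 2.** The hypothesis is comparative: "changes induced by active FES (as measured by brain fMRI and EEG measures) will show greater adaptive brain reorganization changes" than passive FES.
- **Data Processing/Data Analysis, For Specific Aim 2, opening paragraph.** For the laterality measure the arms are compared: "Changes in fMRI and EEG derived LI values over time will be compared in the 2 groups". Mann-Whitney tests at each time point follow. Then, for main effects and a "significant interaction of Group X Time, we will perform Linear Mixed Model analyses".
- **Same section, EEG Data Statistical Analysis.** This paragraph introduces other variables: "The independent variables are the signed r-squared values and the coherence estimates". Two kinds of test are named. The first is general: "Nonparametric statistical tests will be run by calculating Monte-Carlo estimates of the significance probabilities and critical values from the permutation distribution", with FDR correction. The second is reserved for the a priori hypotheses: expected changes in r-squared and coherence "as a result of intervention at C3 and C4 sites will be tested using paired t-tests in MATLAB". No group factor, two-sample test or interaction with time is stated for these two variables.
- **Study Procedures, C) Intervention.** EEG is available in the control arm; for passive FES the plan says "Brain activity will be simultaneously recorded using EEG (electroencephalography) technique".

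**The concern.** A paired t-test asks whether patients differ from themselves between two occasions. Whether it is run in each arm or on all patients together, it does not ask whether active FES changed the EEG more than passive FES did. Practice, growing used to the cap and the task, and the effect of FES itself can occur in both arms, and each would count as change due to the intervention.

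At stake is the interpretation of two mechanistic EEG measures. A significant paired result in the active arm could be reported as reorganization caused by active FES when the passive arm changed just as much. The randomized control that would settle this has EEG recordings, but the plan does not say that they will be used for these measures.

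**Working it through.** **Inputs.** The plan gives no effect size, SD, power or alpha for any EEG measure, so there is no planned EEG figure to reproduce. (The sample size text concerns ARAT only.) From the documents: 72 patients per arm (Randomization), and a 10% allowance for loss (Sample size considerations), giving 72 × 0.9 = 64.8, about 65. Assumed: two-sided 5%, normal change scores, independent arms, and a standardized change dz = mean change / SD of change between 0.20 and 0.40, the same in both arms.

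**Paired test in one arm.** The noncentrality is dz × √n with n − 1 degrees of freedom. For example, n = 65 and dz = 0.20 give 0.20 × √65 = 1.61 against a critical value of 2.00; n = 72 and dz = 0.40 give 0.40 × √72 = 3.39 against 1.99. Call the rejection probability p. With independent arms and equal change, the probability that the active arm is significant and the passive arm is not is p(1 − p). The probability that exactly one arm is significant is 2p(1 − p).

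| n per arm | dz | p, active arm | active only | exactly one arm |
|---|---|---|---|---|
| 65 | 0.20 | 35.5% | 22.9% | 45.8% |
| 65 | 0.25 | 51.0% | 25.0% | 50.0% |
| 65 | 0.40 | 88.8% | 9.9% | 19.9% |
| 72 | 0.20 | 38.8% | 23.7% | 47.5% |
| 72 | 0.25 | 55.3% | 24.7% | 49.4% |
| 72 | 0.40 | 91.7% | 7.6% | 15.2% |

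Simulation with 20,000 runs per setting agrees closely (35% in the first row, 92% in the last). If the test is instead run on all 144 patients together, dz = 0.20 gives 66%.

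**Between-arm test of change in the same setting.** The difference in change, d, is zero, so the noncentrality d × √(n/2) is zero and the test rejects at its nominal 5%. Simulation gave 4.7% to 5.1% throughout.

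**Power of the between-arm test when the arms do differ** (d in SDs of change, 2n − 2 degrees of freedom):

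| n per arm | d | d × √(n/2) | power |
|---|---|---|---|
| 65 | 0.5 | 2.85 | 81% |
| 72 | 0.5 | 3.00 | 85% |
| 65 | 0.3 | 1.71 | 40% |
| 72 | 0.3 | 1.80 | 43% |

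**The case against.** The strongest case on the other side has five parts.

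1. **Aim 2 already has a randomized EEG comparison.** This stands for the EEG-derived LI. A reader might infer that the plan discards the control arm for EEG altogether; it does not. The mixed-model sentence does not itself name LI and comes under a heading that covers brain changes generally. But the sentences before it are about LI, and the EEG paragraph then starts with different variables, so extending the model to r-squared and coherence is not a natural reading.
2. **The permutation tests may compare the arms.** They may. Their contrast is unstated, so a between-arm contrast is neither confirmed nor excluded. One cannot claim that it is absent, only that the a priori C3 and C4 hypotheses are assigned to the paired tests.
3. **A paired test fits a within-patient hypothesis.** True, and the content of these hypotheses is not given. The documents never call the C3 and C4 test confirmatory, and the primary outcome is ARAT, which has its own Group and Time mixed model. What remains is that the tests sit under an aim whose question is comparative.
4. **The 35% to 92% are correct rejections.** This stands. Patients do change in that scenario, so the figures are power. A reader might take them for a false-positive rate. They become misleading only when the result is taken to favour active over passive FES.
5. **The plan does not say that it will contrast significance between arms.** Correct. It does not say whether the paired tests are run per arm or pooled. The figures for active only and for exactly one arm show what that inference would cost if someone drew it; the protocol does not plan it.

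**Conclusion.** The point holds for signed r-squared and coherence at C3 and C4. The only test assigned to their a priori hypotheses does not compare the arms, so it cannot address Aim 2's comparative hypothesis for these measures. The finding does not extend to LI, to the primary ARAT analysis, or to a claim that no permutation test will contrast the arms.

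On size: under equal change in both arms, a significant active-arm result is expected in about 35% to 92% of trials, against about 5% for a between-arm test. This depends on the assumed change of 0.20 to 0.40 SD and on 65 to 72 analysable patients per arm; the documents supply no EEG values to narrow it. That a paired test is silent on the arm difference needs no such assumption. The change should be made, but it concerns a mechanistic analysis and does not threaten the primary comparison.

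**What to change.** For signed r-squared and coherence at C3 and C4, name a between-arm comparison of change as the deciding analysis: either a linear mixed model with a Group by session-phase term, or the late-training value regressed on the early-training value and arm. Two definitions must be fixed in advance:

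- **Early and late values.** The EEG paragraph averages group-level estimates over sessions, so no early or late value exists yet. State which sessions form each.
- **A common task condition.** Cursor control is described only for the active arm. Actual or attempted hand movement alternating with rest is described for both, so base the comparison on that condition.

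State the contrast of the permutation tests. Keep the paired t-tests as descriptive, and say that significance in one arm but not the other is not evidence for Aim 2. Because Aim 2 defines adaptive change as change that correlates with improved outcomes, the between-arm test answers whether change is greater, and the link to outcome still needs its own analysis.

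The cost is a short addition to the analysis section plus these definitions; the recordings are already planned in both arms. The downside is lower power than a within-arm test: about 81% to 85% for a 0.5 SD difference in change, and only 40% to 43% for 0.3 SD. A non-significant result should therefore be reported with its confidence interval and not as evidence of no difference.
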